Continued patient safety assessment will be carried out and all adverse events documented and reported to the WHIRB. On each visit, compliance with treatment will be checked with questions about the side-effects and a subjective evaluation of the tolerability of the administered drug; the patients will also be asked about incidental missed administrations.

Adverse Event Procedures

An adverse event is defined as any untoward medical occurrence in a clinical study subject administered a pharmaceutical product, and which does not necessarily have a causal relationship with the treatment. An adverse event can therefore be any unfavorable or unintended sign (including an abnormal laboratory finding), symptom, or disease that is temporally associated with the use of a pharmaceutical product, whether or not it is considered related to that product. All observed or volunteered adverse events regardless of treatment group or suspected causal relationship to study drug will be recorded in the patient's record. Events involving adverse drug reactions, illnesses with onset during the study, or exacerbations of pre-existing illnesses will be recorded. Exacerbation of pre-existing illness may include worsening or increase in severity of signs or symptoms of the illness, increase in frequency of signs and symptoms of an intermittent illness, or the appearance of a new manifestation/complication. Exacerbation of a pre-existing illness should be considered when a patient/subject requires new or additional concomitant drug or non-drug therapy for the treatment of that illness during the trial. Lack of or insufficient clinical response, benefit, efficacy, therapeutic effect, or pharmacologic action, will not be recorded as an adverse event. The investigator will make the distinction between exacerbation of pre-existing illness and lack of therapeutic efficacy. In addition, clinically significant changes in physical examination findings and abnormal objective test findings (e.g., laboratory, x-ray, ECG) will also be recorded as adverse events. Any abnormal test result that is determined to be an error does not require reporting as an adverse event.

In order to avoid vague, ambiguous, or colloquial expressions, the adverse event term will be recorded using standard medical terminology rather than the subject's own words. Every attempt will be made to describe the adverse event in terms of a diagnosis. All related signs, symptoms and abnormal test results will be grouped together as a diagnosis if applicable and recorded as a single adverse event. All adverse events will be evaluated for intensity and causal relationship with use of the study medication. For all adverse events, sufficient information

should be obtained by the investigator to determine the causality of the adverse event (i.e., study drug or other illness). Follow-up of the adverse event, after the date of therapy discontinuation, is required if the adverse event or its sequelae persist. Follow-up is required until the event or its sequelae resolve or stabilize at a level acceptable to the investigator or his/her designated representative. Clinically significant changes, in the judgment of the investigator, in physical examination findings (abnormalities) will be recorded as adverse events. All subjects who have adverse events, whether or not the adverse events are considered associated with the use of the study medication, will be monitored until the adverse event resolves, stabilizes, or becomes chronic. The clinical course of the adverse event will be followed according to accepted standards of medical practice, even after the end of the observation period, until a satisfactory explanation for the adverse event is found or the investigator considers it medically justifiable to terminate follow-up.

SERIOUS ADVERSE EVENTS: A SERIOUS ADVERSE EVENT (SAE) IS ANY ADVERSE DRUG EXPERIENCE OCCURRING AT ANY DOSE THAT:

1. results in death;
2. is life-threatening (adverse drug experience that places the patient/subject at immediate risk of death from the reaction as it occurred, i.e., it does not include a reaction that, had it occurred in a more severe form, might have caused death);
3. results in inpatient hospitalization or prolongation of existing hospitalization;
4. results in a persistent or significant disability/incapacity (defined as a substantial disruption of a person's ability to conduct normal life functions); or
5. results in congenital anomaly/birth defect.
6. Important medical events that may not result in death, be life-threatening, or require hospitalization may be considered serious adverse drug experiences when, based upon appropriate medical judgment, they may jeopardize the patient/subject and may require medical or surgical intervention to prevent one of the outcomes listed in this definition. Examples of such medical events include allergic bronchospasm requiring intensive treatment in an emergency room or at home, blood dyscrasias or convulsions that do not result in inpatient hospitalization, or the development of drug dependency or drug abuse

The term "severe" is often used to describe the intensity (severity) of a specific event (as in mild, moderate, or severe pain); the event itself, however, may be of relatively minor medical

significance (such as severe headache). By contrast, the term “serious” is used to describe an event based on an event outcome or actions usually associated with events that pose a threat to a patient’s life or functioning. Seriousness (not severity) serves as a guide for defining regulatory reporting obligations. The collection of serious adverse event information will begin at the signing of informed consent and continue through 30 days after administration of the last dose of study medication. Regardless of the above criteria, any additional adverse experiences which an investigator considers serious should be immediately reported. If an SAE occurs, the investigator should initiate appropriate support procedures.

All serious adverse events regardless of treatment group or suspected relationship to study drug must be reported to MedWatch in an expedited manner. The investigator will determine expectedness by referring to the most current version of the Investigator’s Brochure in conjunction with any sponsor-generated IND Safety Reports. Since the trial is being conducted under a physician’s IND, Drs. [name] and [name] are responsible for submitting all IND Safety Reports to the Food and Drug Administration (FDA). The FDA 3500A Form with built-in instructions will be downloaded at: <http://www.fda.gov/medwatch/getforms.htm>. They will also be reported immediately to the Woman’s Hospital Foundation Institutional Review Board at [contact] and Woman’s Health Research Department at [contact]. After submitting an expedited MedWatch 3500A report to the FDA, a courtesy copy will be sent by fax to NovoNordisk. NovoNordisk Safety personnel may fax a follow-up form to the study site to request additional information or clarification of information that was included on the FDA 3500A Report. Queries that address medical issues must be signed by a medically qualified (MD, DO) principal or sub-investigator. In cases where the investigator learns of the SAE after its occurrence and resolution, the time and circumstances of the event will be recorded. The reporting requirements will still be followed.

Any serious adverse event or death will be reported immediately independent of the circumstances or suspected cause if it occurs or comes to the attention of the investigator at any time during the study through the last follow-up visit required by the protocol or 30 days after the last administration of study drug, whichever comes later. Any serious adverse event occurring at any other time after completion of the study will be promptly reported if a causal relationship to study drug is suspected. The only exception to these reporting requirements are serious adverse events that occur during a pre-randomization/washout run-in period, during

which placebo alone or no active study drug or no protocol-specified background drug is administered.

Discontinuations:

The reason for a subject discontinuing from the study will be recorded in the patient chart. A discontinuation occurs when an enrolled subject ceases participation in the study, regardless of the circumstances, prior to completion of the protocol. The investigator must determine the primary reason for discontinuation. Withdrawal due to adverse event will be distinguished from withdrawal due to insufficient response according to the definition of adverse event noted earlier. The final evaluation required by the protocol will be performed at the time of study discontinuation. The investigator will record the reason for study discontinuation, provide or arrange for appropriate follow-up (if required) for such subjects, and document the course of the subject's condition. They will also to be reported to Woman's Hospital Foundation Institutional Review Board at [contact] and Woman's Health Research Department at [contact].

Sample Size Computation and Power Analysis

A priori sample size analysis was performed using the online calculator provided by the Massachusetts General Hospital Mallinckrodt General Clinical Research Center (http://hedwig.mgh.harvard.edu/sample_size/size.html). Because the possible advantages of combination treatment over metformin alone rely on the presumed positive effects of liraglutide on pancreatic β -cell function parameters, we used the difference in a surrogate marker of insulin secretion relative to insulin resistance as the primary outcome for sample size analysis. An experimental design including a total of 118 patients would have power above 0.80 to detect differences in the IS-SI index between treatments such as those previously reported using a similar experimental design.⁴⁶

We plan on recruiting 150 overweight women with a recent history of GDM to be studied. The estimated enrollment: of 75/group for an average follow up of 60 weeks of treatment (range 32-84 weeks) will be our intent-to-treat population. This sample size is projected to provide power ≥ 0.8 to detect a $\geq 20\%$ difference in insulin action indices between treatment groups at a median follow-up of 24 months. The calculation was adapted to allow for significant dropout rate (20-22%) for completion of the full trial of 80 (+4) weeks of treatment. Subjects who drop out of the trial will not be replaced

Statistical Analysis Plan:

The primary outcome measure is the insulin sensitivity-secretion index (IS-SI) and secondary outcome measures include changes in lipid and hepatic enzyme levels, anthropometric parameters, insulin sensitivity and pancreatic β -cell function, and glucose tolerance status. Continuous variables will be tested for normality of distribution using the Kolmogorov-Smirnov test. Natural log transformations of skewed variables will be used where necessary in subsequent analyses. For variables with highly skewed distributions, a logarithmic transformation will be done first and the geometric means reported instead. Differences in effects of drug intervention for continuous variables (in their raw or transformed state) will be compared using Subjects/Drug Treatments by trials analyses of variance (ANOVAs). This analysis provides p values for differences between groups/drug treatments (A), differences over time (B), and the interaction of group/drug treatment with time (AB). Otherwise, changes between baseline and follow-up measurements will be compared between groups by Wilcoxon's nonparametric methods. Anthropometric measurements (body weight, BMI), blood pressure, direct and indirect measurements of carbohydrate metabolism (HOMA, SI_{OGTT} , CIRgp, IGI, and ISSI), and measurements of lipid profile (total cholesterol, HDL, LDL), and liver enzymes (ALT, AST) will be considered as dependent variables. The simultaneous effect of various baseline characteristics and characteristics at certain study treatment intervals between women who did not develop diabetes and women who did during follow-up will be studied with the use of a linear multiple regression analysis. Diabetes and IGT occurrence before and after different treatment will be compared with the McNemar test (complex chi square for paired data), which formally tests for a change between the observed proportions of 2 related samples.

All analyses will be conducted with subjects assigned to their initial treatment group, using all available data for the period of follow-up relevant to the particular analysis. Data will be analyzed on the basis of intention to treat and also on completed treatment parameters where relevant. Differences of $P < 0.05$ will be considered statistically significant. Results will be reported as mean \pm standard error of the mean (S.E.M) for quantitative variables and percentages for categorical variables unless otherwise noted. We will perform all statistical analyses using SPSS 15.0 for Windows (SPSS, Inc.; Chicago, Ill).

Study Drugs

Description

Both active drug (Liraglutide 6.0 mg/ml injection) and placebo will be supplied by Novo Nordisk A/S. as a pre-filled pen for subcutaneous injection. Each liraglutide pre-filled pen contains 18 mg/3 ml (6 mg/ml) and will deliver 30 doses of 0.6 mg; 15 doses of 1.2 mg or 10 doses of 1.8 mg; the placebo pen will deliver equal volumes of vehicle solution only. Liraglutide and placebo are visually identical.

Metformin Hydrochloride XR (extended-release) in 500 mg strength oral tablets will be purchased in bulk through the Woman's Hospital Infusion Pharmacy. Metformin hydrochloride XR is combined with a drug release controlling polymer so that drug is released slowly from the dosage form. The medication will be allocated into appropriate patient dosage regimens by the hospital pharmacy personnel. Dosage of metformin XR will be prescribed according to standard directions and not exceeding the maximum recommended daily dose in adults of 2000 mg.

Trial Supplies

Double-blind Liraglutide or placebo

Liraglutide 6.0 mg/ml or placebo solution for injection in a 3 mL pre-filled pen will be supplied by Novo Nordisk A/S. The pre-filled pen will be provided as a pen-injector. The Investigator will provide each subject with Direction for Use for the liraglutide pen-injector at each dispensing visit.

Packaging and Labelling of Trial Products

Liraglutide and placebo will be packed and labelled by Novo Nordisk A/S and provided in non subject specific boxes. Labelling will be in accordance with Annex 13, local law and trial requirements.

Storage, Handling, Accountability and Destruction of Trial Products

The trial product will be dispensed to each subject as required according to treatment group and under the direction of the study investigator(s). The Investigator will ensure availability of proper storage conditions, and study staff will record and evaluate the temperature (at least every working day). Storage facilities should be checked frequently. A log to document the temperature must be kept on file. No trial product will be dispensed to any person not enrolled in the study.

Storage and in-use conditions

The investigator will provide appropriate instructions to study subjects as to the in-use and not in-use conditions. These instructions will be in accordance with the local regulatory and legal requirements and consistent with the product prescribing information approved by the appropriate regulatory authorities.

Study Timelines

We anticipate that the proposed study will take 36 months (three years) to complete, including 12 months for patient recruitment. Table 1 presents the timetable and key activities in the proposed research.

Target Start Date: January 2011

Table 1

Phase	Tasks
I (Months 1-3)	FDA filing, IRB application, staff training, protocol development, drug and placebo receipt
II (Months 4-16)	Recruitment of women*
III (Months (4-34)	Patient enrollment, treatment, database and data entry, interim analyses if needed
IV (Months (24-36)	Final data entry, data analyses and publication

ADDITIONAL INFORMATION

Woman’s Hospital is one of the largest, not-for-profit women’s specialty hospitals in the United States. The hospital’s most valuable asset is its patient population. Woman’s statistics of over 8100 births (2009), 75,000 pap smears, 47,000 mammograms, 300,000 lab tests, and 13,000

biopsies annually in a centralized location make it ideal for clinical research studies in women's health. The ethnic mix is about 60% Caucasian and 40% African American. In the calendar year of 2009, 600 patients with gestational diabetes delivered at Woman's hospital. The rate of GDM was 7.4% for the year 2009.

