demonstrate dysglycemia (IFG ,IGT or IFG/IGT) and/or β -cell dysfunction that necessitates medication added to diet and exercise intervention will be recruited for the study and thus will not be inclusive of women with diabetes postpartum. The baseline blood samples from the OGTT will also be analyzed for a lipid profile which includes total cholesterol, triglycerides, HDL and LDL cholesterol, TSH, liver enzymes, creatinine with eGFR, and quantitative β hCG levels. A negative serum pregnancy test is a prerequisite for commencing treatment.

All consented patients will come into the outpatient tower for a clinic visit. A full physical examination will be performed including measurement of body mass index (BMI), waist: hip (W: H) ratio and blood pressure (BP). The total body adiposity (total fatness), defined as the accumulation of body fat without regard to regional distribution, will be expressed as BMI and calculated as weight (kg)/ height (m)², whereas the W:H ratio is a measure of body fat distribution. Height will be measured to the nearest centimeter and weight measured by a sliding weight balance to the nearest 0.1 kg. Waist circumference will be measured at the minimum circumference between the rib cage and iliac crest (in centimeters) and hip circumference at the level of the largest circumference around the buttocks by trained clinicians using tape measures from the same manufacturer. The circumference measurements will be taken in the upright position using 15-mm width flexible metric tapes held close to the body but not tight enough to indent the skin. Cardiovascular risk will be assessed biochemically using lipoprotein profile (total cholesterol, triglycerides, HDL, calculated LDL), and by total body fat and its distribution W: H ratio.

Randomization and Allocation

At randomization, all study participants will be assigned to an 80 [+4 weeks] medication treatment group. A computer-generated randomization schedule using a block randomization method will be used. The treatment allocation ratio will be 1:1. Drug will be packaged and labeled according to the randomization schemes. Subjects who are randomized will be assigned the next sequential subject number. Once randomized, the subjects will begin treatment with the allocated study drug or placebo. All personnel involved in the study will be blinded to which treatment arm the patients have been randomized. The drug and placebo will look identical and not have any identifying characteristics.

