Oral glucose tolerance tests with glucose (G) and insulin (I) measured at 0, 30, 60, and 120 after glucose load to assess diabetes, insulin resistance and pancreatic β -cell function will be performed 32 (+4) weeks after study medications are started. Testing will be repeated at 56 (+4) weeks and 80 (+4) weeks after treatment start. The baseline blood samples from the OGTT will also be analyzed for liver enzymes, TSH, creatinine with eGFR (baseline and 56 weeks only), and lipid profile. Subjects will remain on treatment unless they are diagnosed with DM2 during an OGTT or a random blood test at which time final testing will be performed. They will be withdrawn from the study and they will be referred to a specialist for additional treatment of

diabetes. In subjects who complete 80 (+4) weeks of treatment, all study medications will be stopped and subjects will be asked to return for routine OGTT testing by their physician.

Primary Study Endpoint:

- An index of *insulin secretion in relation to insulin resistance (IS-SI)* will be calculated. Thus, β -cell compensatory capacity will be evaluated by the insulin sensitivity-secretion index (IS-SI) defined as the product of composite insulin sensitivity index and first-phase insulin release index (insulinogenic index).

Secondary Study Endpoint(s):

- Indexes of insulin sensitivity and secretion using the serum glucose and insulin concentrations obtained in the fasting state and during the 2hr OGTT with INS will be computed by several measures previously validated in women. Changes in insulin resistance –baseline {HOMA-IR} and composite insulin sensitivity index [ISI_{OGTT}], and pancreatic β -cell function (corrected insulin response [CIR_{glupeak}] and insulinogenic index [IGI])/HOMA-IR
- Anthropometric measurements [BMI, absolute body weight, waist circumference, waist: hip ratio,
- Cardiometabolic risk measures [lipids, liver enzymes; blood pressure]
- Development of diabetes, impaired glucose tolerance or impaired fasting glucose based on positive OGTT. Glucose tolerance will be defined as normal, impaired glucose tolerance (IGT) or diabetic according to the criteria of the American Diabetes Association.¹ Patients diagnosed with diabetes will be withdrawn from the study and referred to a specialized physician.

Biochemical assays and calculations

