Laboratory Measures: Hormonal and metabolic parameters will be measured at baseline (6-52 weeks postpartum), and after 32 (+4) weeks, 56 (+4) weeks and 80 (+4) weeks treatment intervention following an overnight fast. Blood samples will be obtained in the fasting state and ½, 1 and 2 h after a standardized 75-g oral glucose load. Blood samples will be centrifuged, divided into aliquots, and stored at -70°C until assayed. Plasma glucose levels will be determined with a glucose analyzer using the glucose oxidase method (Glucose Reagent Kit, Bayer Newbury, UK). Plasma insulin will be determined in all samples in duplicate by microparticle enzyme immunoassay (Abbott AxSYM System, Abbott Laboratories, Abbott Park,

IL). Levels of total cholesterol, high-density lipoprotein cholesterol (HDL-C) and triglycerides will be determined in the initial basal sample using standard enzymatic colorimetric assays on an automated clinical chemistry analyzer whereas low-density lipoprotein cholesterol (LDL-C) will be calculated according to the Friedewald equation. Serum creatinine, liver enzymes, AST, and ALT will be measured using standard automated kinetic enzymatic assay. Circulating levels of TSH and β hCG will be measured using a two-site sandwich immunoassay with direct chemiluminometric technology (Diagnostic Products, Los Angeles, CA). The intra- and interassay coefficients of variation are less than 7 and 11%, respectively, over the sample concentration range.

Insulin sensitivity and secretion:

Indexes of insulin sensitivity and secretion using the serum glucose and insulin concentrations obtained in the fasting state and during the 2hr OGTT with INS will be computed by several measures previously validated in premenopausal women.³⁵ Insulin resistance/sensitivity will be calculated using homeostasis model assessment (HOMA-IR), which is based on fasting insulin and glucose concentrations³⁶ and the Matsuda insulin sensitivity index, which takes into account mean insulin and glucose levels following oral glucose stimulation.³⁷

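### Glucose-tolerance endpoint: an incident event in the endpoint list, a before/after paired comparison with no named visit in the SAP; under either reading the within-arm McNemar test can show change when nothing changed

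*Combined protocol and SAP*

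**What the plan says.** **Endpoint list** (protocol, Secondary Study Endpoint(s)): "Development of diabetes, impaired glucose tolerance or impaired fasting glucose based on positive OGTT". It does not say which OGTT counts, whether one positive test is enough, or how a woman who enters with IGT or IFG can develop it.

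**SAP** (Statistical Analysis Plan): "Diabetes and IGT occurrence before and after different treatment will be compared with the McNemar test". The test is described as one for paired data. No after visit is named and IFG is not mentioned. No between-arm test is given for glucose-tolerance category; the analysis of variance is for continuous variables.

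**Visits** (text under Randomization and Allocation): the first on-treatment OGTT is "performed 32 (+4) weeks after study medications are started", and "Testing will be repeated at 56 (+4) weeks and 80 (+4) weeks after treatment start". There are therefore three follow-up OGTTs against one baseline OGTT. Participation ends on diabetes but not on IGT or IFG: "Subjects will remain on treatment unless they are diagnosed with DM2 during an OGTT or a random blood test". Women with IGT or IFG go on being retested.

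**Entry** (Study Design): the postpartum OGTT that serves as baseline also decides eligibility. Women qualify if they "demonstrate dysglycemia (IFG ,IGT or IFG/IGT) and/or β -cell dysfunction that necessitates medication", so IGT or IFG at baseline is favoured but not required.

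**Data rule** (end of the Statistical Analysis Plan): "using all available data for the period of follow-up relevant to the particular analysis". This does not choose a visit.

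**The concern.** A McNemar test needs one before value and one after value per woman. The endpoint list suggests an event that may occur at any of three tests; the SAP suggests a state before and a state after. Nothing in the document reconciles them, and they classify women differently:

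- Normal at baseline, IGT at week 32, normal at week 80: a case of development, but unchanged in a baseline-to-week-80 comparison.
- IGT at baseline and at week 80: cannot develop IGT, but counts as an occurrence both before and after.
- New IFG alone: a case in the endpoint list, absent from the SAP test.

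IGT and IFG can revert, so the scoring visit matters in a way it does not for diabetes, which ends participation. With the rule open, it could be settled after results are seen. Repeat testing and selection on the baseline OGTT then push the paired test in opposite directions, and neither push has anything to do with treatment.

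**Working it through.** **Is there a planned figure to reproduce?** Not for this endpoint: the plan gives no rate, power or sample size for it. The enrolment figures used below are coherent: 118 / (1 − 0.21) = 149.4, against the stated 150 (75 per arm) with 20–22% dropout.

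**Inputs from the documents.** One baseline and three follow-up OGTTs; 75 per arm; dropout taken as 21%; P < 0.05 (taken as two-sided). The site's own cohort (Study Background and Rationale) had 24 of 110 women with a glucose abnormality, 24/110 = 21.8%. Among the 98 with any metabolic abnormality this is 24/98 = 24.5%, if the 24 all lie within the 98.

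**Assumptions not in the documents.** The correlation between OGTTs in the same woman, and the proportion abnormal at baseline in the enrolled women. Both are varied.

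**Simple bound.** With a per-test probability of 22%, no true change and independent tests, the chance of at least one abnormal result in three is 1 − (1 − 0.22)³ = 52.5%, against 22% before. Correlation reduces this to 46%, 42%, 37% and 30% at 0.3, 0.5, 0.7 and 0.9.

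**Model.** Each woman has a constant state. At visit j, Z_ij = √ρ·u_i + √(1−ρ)·e_ij, with u and e standard normal; the OGTT is abnormal if Z_ij exceeds the threshold giving prevalence p. Dropouts have one to three follow-up OGTTs, the last at discontinuation. With b women newly abnormal and c no longer abnormal, the exact McNemar P is min(1, 2·Pr[Bin(b + c, ½) ≤ min(b, c)]).

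**Reading 1: any positive follow-up OGTT counts** (75 per arm, underlying p = 25%, nothing changes; ρ = 0.4 / 0.6 / 0.8).

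| Abnormal at baseline | Arms with a false significant result |
|---|---|
| 25% (no enrichment) | worsening 86 / 76 / 57% |
| 40% | worsening 30 / 25 / 17% |
| 50% | worsening about 5% |
| 70% | improvement 22 / 16 / 9% |

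In the first row the any-visit proportion is 46 / 42 / 37%, against 25% at the last OGTT. With p equal at all visits but set to 15% or 40%, false worsening is 68 / 60 / 39% or 93 / 87 / 69%.

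**Reading 2: only the last OGTT counts.** Without enrichment the test rejects in about 3% of arms, both directions together. With baseline abnormality enriched to 40–70%, it falsely shows improvement in 16–99% of arms. A separate run with 59 women per arm, underlying p = 22% and ρ = 0.5 / 0.7 / 0.9 gives the same pattern:

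| Abnormal at baseline | False improvement, baseline versus last OGTT |
|---|---|
| 24.5% | 3 / 2 / 1% |
| 40% | 33 / 25 / 11% |
| 50% | 68 / 54 / 27% |
| 70% | 99 / 96 / 72% |

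This is regression to the mean: at 40% baseline the proportion at one later visit falls to 27–35% with no change in any woman's underlying state.

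**Between arms.** An any-visit comparison of the two arms with equal numbers of OGTTs has a simulated type I error of 4.7%. Unequal follow-up disturbs it: with no treatment effect, 10% versus 32% of women leaving after one OGTT gives 42% versus 38% cases.

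**The case against.** The strongest reply is that the plan never says any visit, first positive or worst of three. Before-and-after wording with a paired test most naturally points to the end-of-treatment OGTT, and on that reading repeat testing adds nothing. This stands as far as it goes. A reader might infer that the plan will count IGT at any of three tests and so is bound to show deterioration. The documents permit that count but do not state it, and the direction is not fixed either: eligibility depends on the baseline OGTT, so enrichment can shrink or reverse the effect. The end-of-treatment reading does not rescue the paired test, because the same selection then produces false improvement.

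A reader might also infer that every comparison on this endpoint is compromised. That is not supported. The trial's question is between arms, and an any-visit comparison between arms is near nominal with equal follow-up. It is affected only if the number of OGTTs differs by arm, and the documents give no reason to expect a particular imbalance. The SAP, however, specifies only the paired test for this endpoint.

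Finally, a single visit is not the only sound definition. Time to first event among women free of the state at baseline would also honour the word development. That is a fair alternative, provided one definition is chosen and the arms are compared.

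**Conclusion.** The point holds as a mismatch between endpoint and analysis, with an unnamed after visit and a paired test that can mislead under either reading. Counting any positive OGTT gives false worsening in about 57–86% of arms if 25% are abnormal at every visit, about 17–30% if baseline abnormality is 40% and about 5% if it is 50%, with false improvement at 70%. Counting the last OGTT is safe without enrichment and gives false improvement with it. These sizes rest on an assumed correlation of 0.4–0.8 and on assumed baseline prevalences. The documents give neither OGTT repeatability nor the expected baseline mix of the enrolled women, so neither the size nor the direction in this trial can be stated. The change should be made, but it concerns one secondary endpoint; the primary IS-SI analysis is untouched.

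**What to change.** Use one definition in the endpoint list and the SAP:

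- Score glucose-tolerance category (normal, IFG, IGT, IFG/IGT, diabetes) at week 80 (+4). For women who leave early, use the final evaluation that the Discontinuations section already requires.
- Carry a woman withdrawn with diabetes as diabetic at the final visit.
- Replace the within-arm McNemar test with a direct comparison of the two arms on that category. Randomisation exposes both arms to the same baseline selection, so regression to the mean does not by itself create a difference between them. Naming the visit while keeping the paired test would not achieve this.
- Report first diabetes at any time as a separate outcome, and the week 32 and week 56 categories descriptively.

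The cost is a few sentences of protocol and SAP text, with no new visits or data. The one loss is that transient IGT or IFG at week 32 or 56 is described rather than counted.
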